9.3 POPULATIONS FOR ANALYSES

Safety Analysis Dataset: the subset of participants who received at least one dose of study intervention.

9.4 STATISTICAL ANALYSES

9.4.1 GENERAL APPROACH

This is a safety and feasibility study that is designed to evaluate the safety and feasibility of IFx-Hu2.0 use as monotherapy. Safety will be assessed and reported based upon CTCAE v5.0 criteria. Feasibility will be defined as the ability to treat at least 80 of the 100 patients enrolled without dose-limiting toxicity.

The secondary endpoint is Pathological Response defined as a response assessment to IFx-Hu2.0 in tumor lesions excised at four weeks as; pathological complete response (pCR), major pathological response (mPR), partial pathological response (pPR), or pathological non-response (pNR) by evaluating percent Residual Vial Tumor (%RVT)(15).

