1 PROTOCOL SUMMARY

1.1 SYNOPSIS

Title:	Phase 1 Trial of IFx-Hu2.0 to Evaluate Safety in Patients with Skin Cancer
Study Description:	One hundred patients will receive IFx-Hu2.0 on an outpatient basis at a single time point in a single lesion. These patients will be assessed for any immediate adverse reactions and at Week 4 (Day 28+-5 days) for any delayed adverse events.
Objectives:	
Primary Objective: To assess safety and feasibility
 
Secondary Objective: To assess post-therapeutic pathological response
 
Tertiary/Exploratory Objective: To assess anti-tumor immunity post-treatment.

Endpoints:	
Primary Endpoint: The primary endpoints of this trial will be the safety and feasibility of the treatment regimen. Safety will be reported using the most current version of the Common Terminology Criteria for Adverse Events (CTCAE). Feasibility will be defined as the ability to treat at least 85 of the approximate 100 patients enrolled without investigational product (IP) related dose-limiting toxicity (DLT).
 
Secondary Endpoints: The secondary endpoint is Pathological Response defined as a response assessment to IFx-Hu2.0 in tumor lesions excised by evaluating percent Residual Vial Tumor (%RVT), at four weeks as:
 
• pathological complete response (pCR),• major pathological response (mPR),• partial pathological response (pPR), or• pathological non-response (pNR) 
Tertiary/Exploratory Endpoints: Patient samples (plasma and/or serum) will be assayed to detect tumor antigen specific antibody generation in addition to a protein biomarker discovery assay specific to immuno-oncology therapy assessments. IHC will be performed on pre- and post-treatment tissue samples to contrast the cell sub-types across time points.

Study Population:	Adult male or female subjects with confirmed cutaneous squamous cell carcinoma, or basal cell carcinoma with lesions accessible for intralesional injection.
Phase:	Phase 1
Description of Sites/Facilities Enrolling Participants:	Approximately 5 NCI-designated cancer centers, academic medical centers, clinics, and doctor's offices within the United States, qualified to perform clinical studies under GCP.
Description of Study Intervention:	Plasmid DNA encoding a Streptococcal antigen in a cationic polymer-based solution in doses of 100 µg delivered intralesionally at a single time point "Week 0".
Study Duration:	12 Months
Participant Duration:	Up to six weeks

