3 OBJECTIVES AND ENDPOINTS

OBJECTIVES	ENDPOINTS
Primary	
Safety; i.e., to assess the safety, tolerability, and feasibility of treatment with IFx-Hu2.0 as a monotherapy in patients with skin cancer.
 
The primary endpoints of this trial will be the safety and feasibility of the treatment regimen. Safety will be reported using the most current version of Common Terminology Criteria for Adverse Events (CTCAE).
 
Feasibility will be defined as the ability to treat at least 80 of the approximately 100 patients enrolled without dose-limiting toxicity (DLT).

Secondary	
To assess post-therapeutic pathological response at four weeks post-treatment.
 
The secondary endpoint is Pathological Response defined as a response assessment to IFx-Hu2.0 in tumor lesions excised by evaluating percent Residual Vial Tumor (%RVT), at four weeks as:
 
• pathological complete response (pCR),• major pathological response (mPR),• partial pathological response (pPR), or• pathological non-response (pNR)
Tertiary/Exploratory	
To assess anti-tumor immunity post-treatment.
 
Patient samples (plasma and/or serum) will be assayed to detect tumor antigen specific antibody generation in addition to a protein biomarker discovery assay specific to immuno-oncology therapy assessments.
 
IHC will be performed on pre- and post-treatment tissue samples to contrast the cell sub-types across time points.

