5.5 STRATEGIES FOR RECRUITMENT AND RETENTION

This study will have a goal of 100 evaluable patients. It is the intent of the study team to recruit additional patients to be screened and enrolled if any of the existing patients are lost to follow-up or withdraw consent.

Potential participants will be identified by sites through physician referrals, available recruitment databases, and other methods available to participating sites to identify potential participants. Specific recruitment materials may be developed by the sponsor. In addition, if any site decides to utilize participant-focused materials for recruitment, such materials and a usage plan will be submitted for IRB review and approval prior to implementation. A clinical enrollment manager (CEM) or sponsor designee(s) may locally support the research team and facilitate patient recruitment at the study site in addition to all other measures/efforts. Under no circumstance will referral fees, incentives, or bonuses to physicians for recruitment be allowed.

There is no specific plan to target participants based on race, gender, or age. All eligible potential participants will be approached for inclusion.

It is anticipated that recruitment will take up to 12 months to complete at approximately five research sites. Sites will be NCI-designated cancer centers, academic medical centers, clinics, and doctor's offices within the United States. Sites can include community facilities as a primary site or a satellite site of a participating center as long as they meet the requirements regarding the proper handling and administration of the investigational agent.

Due to the size and short duration of the study, there is no planned retention or compensation plan for participants. Throughout the study, participants will be reminded about upcoming visits and the procedures to be performed at the visit. New information that surfaces during the study will be communicated to participants through IRB-approved mechanisms.

In alignment with the Internal Revenue Service (IRS) 2020 Standard Mileage Rate (Notice 2020-05), participants can be reimbursed at a rate of 17 cents per mile driven in an automobile for traveling for study-related medical purposes. This will be done approximately one month after travel receipts are submitted by study staff to the sponsor.

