9.4.2 SAFETY ANALYSES

Maximum planned sample size	100
The event probability (ϑ)	0.2
Desired probability of early stopping	0.05

The trial will be stopped if the number of Dose Limiting Toxicities (DLTs) is equal to or exceeds b_n out of n patients with completed follow-up.

Number of Patients, n	1	2	3	4	5	6	7	8	9	10	11	12	13	14	15	16	17	18	19	20
Boundary, b_n	-	-	3	4	4	5	5	6	6	6	7	7	7	8	8	8	9	9	9	10
Number of Patients, n	21	22	23	24	25	26	27	28	29	30	31	32	33	34	35	36	37	38	39	40
Boundary, b_n	10	10	11	11	11	11	12	12	12	13	13	13	13	14	14	14	15	15	15	15
Number of Patients, n	41	42	43	44	45	46	47	48	49	50	51	52	53	54	55	56	57	58	59	60
Boundary, b_n	16	16	16	17	17	17	17	18	18	18	18	19	19	19	20	20	20	20	21	21
Number of Patients, n	61	62	63	64	65	66	67	68	69	70	71	72	73	74	75	76	77	78	79	80
Boundary, b_n	21	21	22	22	22	22	23	23	23	23	24	24	24	24	25	25	25	25	26	26
Number of Patients, n	81	82	83	84	85	86	87	88	89	90	91	92	93	94	95	96	97	98	99	100
Boundary, b_n	26	26	27	27	27	27	28	28	28	28	29	29	29	29	30	30	30	30	31	31

This boundary is equivalent to testing the null hypothesis, after each patient, that the event rate is equal to 0.2, using a one-sided level 0.008340 test.

Sequential boundaries will be used to monitor dose-limiting toxicity rate. The accrual will be halted if excessive numbers of DLTs are seen, that is, if the number of DLTs is equal to or exceeds b_n out of n patients with full follow-up. This is a Pocock-type stopping boundary that yields the probability of crossing the boundary at most [probability of early stopping] when the rate of DLTs is equal to the acceptable rate [event probability θ] (16).

θ	ϕ^*	$E[Y]$	$SD[Y]$	$E[N]$	$SD[N]$	$E[Y/N]$	$SD[Y/N]$
0.20	0.0497	19.31	4.40	96.58	16.21	0.21	0.10
0.30	0.6116	20.12	7.86	67.08	34.29	0.37	0.16
0.40	0.9883	11.85	6.31	29.65	22.10	0.50	0.18
0.50	1.0000	7.61	3.56	15.22	10.91	0.61	0.19
0.60	1.0000	5.71	2.31	9.52	6.29	0.71	0.19
0.70	1.0000	4.62	1.63	6.60	3.96	0.79	0.17
0.80	1.0000	3.89	1.14	4.86	2.51	0.87	0.14
0.90	1.0000	3.37	0.69	3.74	1.41	0.94	0.11
1.00	1.0000	3.00	0.00	3.00	0.00	1.00	0.00

Definitions:

Y = the number of events, random, between 0 and N

N = the number of patients, random, between 1 and K

ϕ^* = the actual probability of early stopping (hitting the boundary)

$E[]$ denotes the expected value (mean)

$SD[]$ denotes the standard deviation

Resource: <http://cancer.unc.edu/biostatistics/program/ivanova/ContinuosMonitoringForToxicity.aspx>

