2. ELABORATION OF STUDY PROTOCOL

2.1 Study Populations

- Safety Analysis Dataset: the subset of participants who received at least one dose of study intervention (IFx-Hu2.0). All safety analyses will be conducted on Safety Analysis Set.

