3.4. Handling of Missing Data

Missing data will not be imputed for safety analyses.

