3.8. Change to Planned Protocol Analysis

Not applicable.

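### Feasibility, a primary endpoint, has two cut-offs in current text (85 and 80 of about 100 patients without a DLT), and nothing says which one governs

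*Protocol*

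**What the plan says.** Four current passages define feasibility.

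- Protocol 1.1 (synopsis): "the ability to treat at least 85 of the approximate 100 patients enrolled without investigational product (IP) related dose-limiting toxicity". SAP 2.2.1 sets the same cut-off of 85.
- Protocol 9.4.1: "Feasibility will be defined as the ability to treat at least 80 of the 100 patients enrolled without dose-limiting toxicity". Protocol section 3 also says 80, but of approximately 100.

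The amendment history (protocol 10.3) does not mention the cut-off. SAP 3.8, on changes to the protocol's planned analysis, says "Not applicable".

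Several passages bear on the denominator.

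- Protocol 5.5: "This study will have a goal of 100 evaluable patients". Protocol 7.2 says treated patients who later withdraw or are withdrawn will be replaced.
- SAP 2.1: "All safety analyses will be conducted on Safety Analysis Set", meaning everyone who received a dose.
- Protocol 9.4.2 counts DLTs for the stopping boundary "out of n patients with completed follow-up".
- SAP 3.4: "Missing data will not be imputed for safety analyses".

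The DLT definition also varies. Protocol 9.2 and SAP 2.3 require the event to be judged an unacceptable toxicity by the principal investigator and/or the medical monitor. SAP 2.2.1 and 3.7 have no such condition.

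**The concern.** A primary endpoint with a pass mark needs one pass mark, fixed before the data are seen. Here a reader of the synopsis or the SAP and a reader of the protocol's endpoint and statistics sections could reach opposite conclusions from the same data. The trial is open-label, so the choice could be made with the DLT count already known.

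Only the 85 wording says the toxicity must be related to the investigational product. That does not explain the two numbers, because every DLT definition in the documents already requires at least possible relatedness.

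The count being compared with the cut-off is itself loosely defined. No passage names the denominator for feasibility, or says how to count a treated patient who leaves before the 4-week DLT window is complete.

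**Working it through.** **Inputs.** Cut-offs of 85 (protocol 1.1, SAP 2.2.1) and 80 (protocol 3, 9.4.1). N = 100 assessed patients, from the target of about 100. Stopping boundary from protocol 9.4.2: acceptable rate 0.2, one-sided level 0.008340 after each patient, 31 DLTs at n = 100. The true DLT rate p is an assumption, because the documents state no expected rate.

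**The plan's own figure.** The cut-offs are definitions and are not derived from a formula, so the computed figure to reproduce is the stopping boundary. Taking for each n the smallest r with P(X ≥ r | n, 0.2) ≤ 0.008340 reproduces all 100 printed entries, including 31 at n = 100. The exact probability of crossing at a rate of 0.2 is 0.0490, against the printed 0.0497. That small difference has no bearing here.

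**Where the rules disagree.** With X patients having a DLT out of 100:

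- 85 rule: feasible if 100 − X ≥ 85, so X ≤ 15.
- 80 rule: feasible if 100 − X ≥ 80, so X ≤ 20.

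They agree for X ≤ 15 (both feasible) and X ≥ 21 (neither feasible). They disagree for X = 16, 17, 18, 19 and 20. All five counts are below 31, so the trial can finish there.

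**How likely that is.** X ~ Binomial(100, p), and P(16 ≤ X ≤ 20) = P(X ≤ 20) − P(X ≤ 15). The last column applies the 9.4.2 boundary after every patient, by exact recursion, and counts only trials that reach 100.

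| Assumed p | P(X ≤ 15): 85 rule met | P(X ≤ 20): 80 rule met | P(16 to 20) | P(16 to 20), with boundary |
|---|---|---|---|---|
| 0.05 | 0.99996 | 1.0000 | 0.00004 | 0.00004 |
| 0.10 | 0.9601 | 0.9992 | 0.0391 | 0.0388 |
| 0.15 | 0.5683 | 0.9337 | 0.3654 | 0.3616 |
| 0.18 | 0.2630 | 0.7475 | 0.4845 | 0.4789 |
| 0.20 | 0.1285 | 0.5595 | 0.4310 | 0.4256 |
| 0.25 | 0.0111 | 0.1488 | 0.1377 | 0.1358 |

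**What earlier human data say about p.** The prior study reported no grade 3 to 5 treatment-related events in 6 evaluable patients. The one-sided 95% exact upper limit is 1 − 0.05^(1/6) = 0.39, so rates of 0.15 to 0.20 are not excluded.

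**Effect of the denominator (assumed numbers).** Suppose 100 patients complete follow-up and 16 have a DLT, leaving 84 without, which fails a cut-off of 85. Now add replaced patients with incomplete windows and count them as DLT-free.

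- Cut-off read as a count, as written: one added patient gives 84 + 1 = 85, which passes.
- Cut-off read as 85%: seven are needed, since 16/106 = 15.09% fails and 16/107 = 14.95% passes.

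For the 80 rule, take 21 DLTs among 100, leaving 79.

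- Read as a count: one added patient gives 80, which passes.
- Read as 80%: five are needed, since 21/104 = 20.19% fails and 21/105 = 20.0% passes.

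None of these figures measures the effect of the two DLT definitions. The documents give no basis for that.

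**The case against.** The best case on the other side concerns weight. This is a single-arm phase 1 study. No test, interval or planned table is tied to the feasibility cut-off, accrual is governed by a boundary that uses neither 80 nor 85, and SAP 3.2.1 reports the DLT rate with a 95% CI in any event. The disagreement needs exactly 16 to 20 DLTs in 100, and the only human data cited show none of the relevant events in 6 patients. All of that is true, and no data would be lost. What remains undefined is the pre-specified conclusion on a primary endpoint. The data on 6 patients are too few to rule out the rates at which the conflict matters, and the protocol's own acceptable rate for monitoring, 0.2, is near the peak.

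On the denominator, it is fair that monitoring counts only completed follow-up while the final analysis uses all treated patients. Such a difference is normal and does not by itself contradict anything. The percentage illustration does read the cut-offs as proportions, whereas the documents state counts, and its numbers of incomplete patients are invented. Read as counts, though, the result is more sensitive, since one patient is enough. The narrower gap stands: feasibility has no named denominator and no rule for incomplete windows.

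SAP 3.8 is weak evidence, because the SAP's 85 does agree with the synopsis. It shows only that precedence is unstated. The 0.2 monitoring rate matches the 80 version numerically, but no passage links the two. The DLT-definition conflict is a distinct defect that also reaches the DLT rate and the stopping rule. It is raised here because it changes the same count.

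**Conclusion.** The concern holds and should be fixed before analysis. With exactly 100 patients assessed, 16 to 20 patients with a DLT gives opposite feasibility conclusions depending on the section read. At a true rate of 0.15 the chance of declaring feasibility is 0.57 under one rule and 0.93 under the other; at 0.20 it is 0.13 and 0.56 (both ignoring early stopping). If DLTs are rare, at 0.05 or below, the conflict will almost certainly not matter in practice.

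These probabilities rest on assumed true rates, independent patients and exactly 100 assessed. The seriousness rests on a primary endpoint having two definitions, and does not depend on the probability of landing in the gap. The documents do not settle which cut-off was intended.

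**What to change.** Before the data are analysed, the sponsor should:

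1. Reconcile protocol 1.1, 3 and 9.4.1 and SAP 2.2.1 to one cut-off, written as a proportion of a stated denominator.
2. Name that denominator and say how it relates to the Safety Analysis Set (SAP 2.1) and to the completed-follow-up count in protocol 9.4.2.
3. State how treated patients who leave before completing the 4-week DLT window, and are replaced under protocol 7.2, are counted, so that they do not become DLT-free by default.
4. Reconcile protocol 9.2 and SAP 2.2.1, 2.3 and 3.7 to one DLT definition.

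Optionally, give the probability of passing at several true DLT rates, and say how the cut-off relates to the 0.2 monitoring rate.

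The cost is wording in two documents, with no extra patients or data.

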9.4.2 SAFETY ANALYSES

Maximum planned sample size	100
The event probability (ϑ)	0.2
Desired probability of early stopping	0.05

The trial will be stopped if the number of Dose Limiting Toxicities (DLTs) is equal to or exceeds b_n out of n patients with completed follow-up.

Number of Patients, n	1	2	3	4	5	6	7	8	9	10	11	12	13	14	15	16	17	18	19	20
Boundary, b_n	-	-	3	4	4	5	5	6	6	6	7	7	7	8	8	8	9	9	9	10
Number of Patients, n	21	22	23	24	25	26	27	28	29	30	31	32	33	34	35	36	37	38	39	40
Boundary, b_n	10	10	11	11	11	11	12	12	12	13	13	13	13	14	14	14	15	15	15	15
Number of Patients, n	41	42	43	44	45	46	47	48	49	50	51	52	53	54	55	56	57	58	59	60
Boundary, b_n	16	16	16	17	17	17	17	18	18	18	18	19	19	19	20	20	20	20	21	21
Number of Patients, n	61	62	63	64	65	66	67	68	69	70	71	72	73	74	75	76	77	78	79	80
Boundary, b_n	21	21	22	22	22	22	23	23	23	23	24	24	24	24	25	25	25	25	26	26
Number of Patients, n	81	82	83	84	85	86	87	88	89	90	91	92	93	94	95	96	97	98	99	100
Boundary, b_n	26	26	27	27	27	27	28	28	28	28	29	29	29	29	30	30	30	30	31	31

This boundary is equivalent to testing the null hypothesis, after each patient, that the event rate is equal to 0.2, using a one-sided level 0.008340 test.

Sequential boundaries will be used to monitor dose-limiting toxicity rate. The accrual will be halted if excessive numbers of DLTs are seen, that is, if the number of DLTs is equal to or exceeds b_n out of n patients with full follow-up. This is a Pocock-type stopping boundary that yields the probability of crossing the boundary at most [probability of early stopping] when the rate of DLTs is equal to the acceptable rate [event probability θ] (16).

θ	ϕ^*	$E[Y]$	$SD[Y]$	$E[N]$	$SD[N]$	$E[Y/N]$	$SD[Y/N]$
0.20	0.0497	19.31	4.40	96.58	16.21	0.21	0.10
0.30	0.6116	20.12	7.86	67.08	34.29	0.37	0.16
0.40	0.9883	11.85	6.31	29.65	22.10	0.50	0.18
0.50	1.0000	7.61	3.56	15.22	10.91	0.61	0.19
0.60	1.0000	5.71	2.31	9.52	6.29	0.71	0.19
0.70	1.0000	4.62	1.63	6.60	3.96	0.79	0.17
0.80	1.0000	3.89	1.14	4.86	2.51	0.87	0.14
0.90	1.0000	3.37	0.69	3.74	1.41	0.94	0.11
1.00	1.0000	3.00	0.00	3.00	0.00	1.00	0.00

Definitions:

Y = the number of events, random, between 0 and N

N = the number of patients, random, between 1 and K

ϕ^* = the actual probability of early stopping (hitting the boundary)

$E[]$ denotes the expected value (mean)

$SD[]$ denotes the standard deviation

Resource: <http://cancer.unc.edu/biostatistics/program/ivanova/ContinuosMonitoringForToxicity.aspx>

The medical monitor will provide recommendations for proceeding with the study to the clinical team and study sponsor. The study sponsor will inform the FDA of the temporary halt and the disposition of the study.

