1.2 SCHEMA

1.3 SCHEDULE OF ACTIVITIES (SOA)

Procedure	Screening Visit Day -14 to -1	Baseline Visit Week 0/Day 0	DLT Follow up Week 4/Day 28 +/-5 days	Unscheduled Visit	Early Termination Visit
Informed consent	X				
Demographics	X				
Medical History	X				
Physical exam w/vitals	X	X	X	X	X
Performance Status	X	X	X	X	X
Tumor Burden (lesion measurements)	X	X	X	X	X
Concomitant medications review	X	X	X	X	X
Electrocardiogram (ECG)	X		X	X	X
Pathology Report Confirming Diagnosis (specific to lesion marked for injection)	X				
Clinical laboratory samples (safety) ^a	X	X	X	X	X
Pregnancy test	X ^b	X ^c	X ^b	X ^b	X ^b
Blood for Immune Response Evaluation		X	X	X	X
IFx-Hu2.0 dosing		X			
Adverse event review and evaluation		X	X	X	X
Tumor excision for pathological response (final)			X		X

^a **Clinical laboratory samples (safety);** samples will include blood and urine for the following tests:

- Hematology: CBC - hemoglobin, hematocrit, white blood cells (WBC) with differential count, platelet count; blood clotting tests: prothrombin time (PT) and activated partial thromboplastin time (aPTT)
- Biochemistry: CMP - glucose, calcium, albumin, total protein, sodium, potassium, CO2, chloride, BUN, creatinine, total bilirubin, alanine aminotransferase (ALT), aspartate aminotransferase (AST), alkaline phosphatase (ALP), lactate dehydrogenase (LDH), Thyroid tests (TSH and FT4)
- Serology: Hepatitis B Core Antibody (IgM), Hepatitis C Antibody (Anti-HCV), HIV-1/2 Antigen and Antibodies
- Urinalysis: UA with microscopic evaluation
- Anti-double-stranded DNA (anti-dsDNA) antibody test
- Anti-DNase B Titer, Serum

^b **Serum pregnancy test** – indicated only in women of childbearing potential

^c **Urine pregnancy test** done within 24 hours prior to IFx-Hu2.0 administration and results must be available prior to IFx-Hu2.0 administration, – only in women of childbearing potential

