8.2.5 ADVERSE EVENT REPORTING

Adverse events will be documented. The principal investigator at the site is responsible for notifying the sponsor of any adverse event as soon as possible. The medical monitor will review all adverse event reports and ensure that participants are receiving appropriate clinical care and identify any potential safety concerns. The medical monitor will assess the information provided to determine the relatedness of the event to the study intervention as well as propose any changes to the protocol and/or consent form based on the event. All adverse events will be documented and reported to the FDA in the annual report. Adverse events that meet the requirements for reporting to the IRB will be reported within the guidelines required by the IRB of record, along with necessary supporting information and revised trial documentation, as necessary.

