9.2 SAMPLE SIZE DETERMINATION

The intent of this study is to enroll approximately 100 evaluable patients to assess the safety of IFx-Hu2.0 as a monotherapy. A sample size of 100 has the following precision for estimation of DLT rates ranging from 0.1 to 0.5. A DLT is defined as an adverse event equal to or greater than grade 3, at least possibly related to the investigational agent, occurring within a 4-week period following IP administration, and deemed as having unacceptable toxicity by the principal investigator and/or medical monitor. Precision is measured by 1-sided 95% upper confidence limit on the estimated DLT rate via exact binomial distribution. For example, if no DLT is observed in patients on IFX-Hu 2.0, then the true underlying DLT rate is lower than 0.099 with 95% confidence.

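### The DLT boundary counts only participants with completed follow-up while dosing continues, so about 7 more are dosed before a halt than the printed E[N] when the true DLT rate is 0.40 or more

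*Protocol*

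**What the plan says.** Protocol 9.4.2 sets a Pocock-type boundary for at most 100 participants, with acceptable DLT rate 0.2 and early-stopping probability 0.05. The trigger is met when the number of DLTs "is equal to or exceeds b_n out of n patients with completed follow-up". The section then restates the rule in terms of full follow-up and gives the consequence: "The accrual will be halted if excessive numbers of DLTs are seen". Its table of operating characteristics prints E[N], with the definition "N = the number of patients, random, between 1 and K".

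The time scale is set elsewhere. Under Protocol 9.2 a DLT is an event "occurring within a 4-week period following IP administration". The Schedule of Activities (1.3) closes that window at the visit headed "DLT Follow up Week 4/Day 28 +/-5 days". On recruitment, Protocol 5.5 says: "It is anticipated that recruitment will take up to 12 months to complete at approximately five research sites". No section staggers or pauses accrual while participants are in follow-up. The SAP does not mention the boundary, and its section 3.6 plans no interim analysis.

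**The concern.** A DLT is usually known well before Week 4. Under Protocol 8.2.5 the site investigator is "responsible for notifying the sponsor of any adverse event as soon as possible". The boundary nevertheless ignores the event until that participant's follow-up is complete, and dosing goes on meanwhile.

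The delay hardly matters when DLTs are rare. It matters when they are frequent, which is the case the boundary exists for. Someone reading E[N] beside a statement that accrual is halted could take it as the expected exposure before a halt. At high DLT rates that understates both the number dosed and the number with a DLT.

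**Working it through.** **Inputs.** K = 100, acceptable rate 0.2, one-sided level 0.008340, the b_n table and E[N] (Protocol 9.4.2); a 4-week window closed at Day 28 ± 5 (9.2 and 1.3); about 100 participants in up to 12 months (5.5). Even accrual is an assumption. The documents give no DLT onset times, so these are assumed and a range is shown.

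**1. Reproduce the plan.** Take b_n as the smallest r with P(X ≥ r) ≤ 0.008340 for X ~ Binomial(n, 0.2). All 100 printed values match. An exact recursion, with each outcome known before the next participant is dosed, gives:

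| True rate | P(cross), exact / printed | E[N], exact / printed |
|---|---|---|
| 0.20 | 0.0490 / 0.0497 | 96.60 / 96.58 |
| 0.30 | 0.6137 / 0.6116 | 67.10 / 67.08 |
| 0.40 | 0.9878 / 0.9883 | 29.59 / 29.65 |
| 0.50 | 1.0000 / 1.0000 | 15.23 / 15.22 |

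The differences are of the size expected from simulation. The printed E[N] therefore has no term for participants dosed but still in follow-up.

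**2. Add the follow-up lag.** Spacing is 365/100 = 3.65 days, and 28/3.65 = 7.67, so 7 more participants are dosed before participant N completes follow-up. The number dosed at the halt is min(N + 7, 100).

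| True rate | Mean dosed | Printed E[N] |
|---|---|---|
| 0.20 | 96.9 | 96.58 |
| 0.30 | 71.3 | 67.08 |
| 0.40 | 36.5 | 29.65 |
| 0.50 | 22.2 | 15.22 |
| 1.00 | 10.0 | 3.00 |

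Mean participants with a DLT = rate × mean dosed: 0.40 × 36.48 = 14.6 against printed E[Y] 11.85, and 0.50 × 22.23 = 11.1 against 7.61.

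**3. Sensitivity at 0.40.** Closing follow-up at Day 23 or Day 33 (6 or 9 dosed meanwhile) gives 35.5 or 38.4. Poisson arrivals give 37.1 to 37.4. Accrual in 6 months (assumed; the protocol says up to 12) gives 44.3.

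**4. Same b_n in dosing order.** Halt when the DLTs known so far among the first j dosed reach b_j, for any j. The known count in that set never exceeds its final count, so any such crossing also occurs under the printed rule, and never sooner there. This needs no leavers and no reversed DLTs. Simulated with 20,000 trials per cell:

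| Assumed onset | Mean dosed at 0.40 | Saving | Mean dosed at 0.50 | Saving |
|---|---|---|---|---|
| Uniform, days 0–28 | 33.6 | 36.5 − 33.6 = 2.9 | 19.3 | 22.2 − 19.3 = 2.9 |
| Uniform, days 0–7 | 30.1 | 36.5 − 30.1 = 6.4 | 15.6 | 22.2 − 15.6 = 6.6 |
| All on Day 28 | 36.5 | 0 | 22.2 | 0 |

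With an assumed 7-day delay for review, the saving at 0.40 is about 0.5 to 4.5. These are simulated means, so the low end is uncertain by a few tenths.

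**5. Leavers.** Suppose the dosing-order rule replaced the printed check and leavers without a DLT counted as DLT-free. If a fraction L leaves at a uniform time and onset is uniform, the observed rate is p(1 − L/2). At p = 0.30, L = 0.05 gives 0.30 × 0.975 = 0.2925 and P(halt) 0.56; L = 0.10 gives 0.30 × 0.95 = 0.285 and P(halt) 0.50. Without leavers it is 0.61.

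**The case against.** **E[N] is not misprinted.** The rule's n is explicitly participants with completed follow-up, and the table never claims to count everyone dosed. A reader might infer that the table is wrong or that the 0.05 limit is breached. Neither follows: both columns reproduce, and the delay does not change which trials cross.

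**Waiting has a purpose.** A DLT under Protocol 9.2 needs a grade, an attribution and a judgement that the toxicity is unacceptable; 8.2.3.2 lets attribution change as information arrives. Completed follow-up is a reasonable way to count settled outcomes. If 2% or 5% of DLT-free participants were provisionally called DLTs and not reversed before a halt (assumed), crossing at 0.20 could reach 0.086 or 0.18. This stands, and it is why only adjudicated DLTs should feed an early trigger.

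**Other safeguards exist.** Serious events are reported immediately (8.2.6), the medical monitor reviews data continuously (10.1.6), and the study can be suspended for unacceptable risk (10.1.2). It would be wrong to infer that dosing must continue until the boundary is crossed. These safeguards are discretionary, with no stated threshold or error rate, and they do not change how the boundary counts.

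**High rates look unlikely.** The earlier human trial saw no grade 3 to 5 treatment-related event in six evaluable patients (2.3.1); at a true rate of 0.40 the chance of that is 0.6^6 = 0.047. That population had advanced melanoma, so this is reassuring but not conclusive.

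**Conclusion.** The concern holds as a gap between the number the boundary counts and the number exposed. At even accrual over 12 months with 28-day follow-up, the excess over E[N] is about 7 at true DLT rates of 0.40 and above, about 4 at 0.30, and about 0.3 at 0.20. Faster accrual would widen it.

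The printed boundary and its operating characteristics are correct for the rule as written. A reader might also infer that counting in dosing order leaves the crossing probabilities unchanged whatever happens. That is so only with no leavers and no later reversal of a DLT. The gain rests on assumed onset times and review speed and may be small. This is a cheap improvement worth making, not an error that undermines the design.

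**What to change.** In Protocol 9.4.2, keep b_n and the completed-follow-up check, and add:

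- Number participants in dosing order across all sites. Halt accrual as soon as the DLTs among the first j dosed, each already judged a DLT under the 9.2 definition, reach b_j, without waiting for the rest of those j to finish follow-up.
- Say that the DLTs and j refer to the same first j participants. Looser wording changes the error rate. Setting all known DLTs against b_n at the number with completed follow-up gives a crossing probability at 0.20 of about 0.24 (simulated, uniform onset).
- Beside E[N], print the expected number dosed at the planned accrual.

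Keeping the printed check avoids the loss of detection from leavers. With leavers, the two checks run on slightly different sets, so the pair can cross slightly more often than either alone. The crossing probability at 0.20 should be recomputed for the pair, stating whether replacements under 7.2 are covered.

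The cost is a few sentences, a running dosing order across about five sites, and prompt adjudication; no new data are needed. The remaining downside is a halt on a DLT that is later reclassified. 9.4.2 already treats the halt as provisional: "The study sponsor will inform the FDA of the temporary halt and the disposition of the study".
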